1.2 Study Rationale and Aim

The **E**ffectiveness of **D**aily **S**tep-based **E**xercise **T**herap**Y** Using **F**ITness **M**onitors for **P**eripheral **A**rtery **D**isease (**EASY FIT**) Trial will be a single-center prospective non-inferiority randomized controlled trial comparing the efficacy of a novel 12-week daily step-based exercise program vs. the efficacy of a standard guideline-recommended symptom-based exercise program, on improving walking ability in patients with symptomatic lower extremity peripheral artery disease (PAD). We will enroll and randomize 40 patients to a novel 12-week step-based exercise program or a standard guideline-recommended 12-week symptom-based exercise program. To date, we believe that our study is the first to investigate the efficacy of a 12-week daily step-based exercise program on improving walking ability in patients with symptomatic lower extremity PAD. As such, our clinical investigation is a pilot study and will aim to assess the efficacy, safety, and feasibility of a novel daily step-based exercise program for this particular patient population. We believe that this pilot study will generate data for a larger trial in the future.

Compared to the standard guideline-recommended symptom-based exercise program, we hypothesize that a daily step-based exercise program using fitness monitors will be non-inferior in improving walking ability and quality of life for patients with symptomatic lower extremity PAD. We also hypothesize that a daily step-based exercise program will be safe and feasible.

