3.1 Inclusion Criteria

Patients are eligible for enrollment if they meet all of the following criteria.

1. Male or female with an age of 18 years or older
2. Diagnosis of lower extremity PAD, based on at least 1 of the following criteria:
 - Ankle-brachial index (ABI) of 0.9 or less in one or both legs
 - Invasive angiography demonstrating obstructive lower extremity artery disease
 - History of prior endovascular or surgical revascularization of lower extremity artery
3. Symptomatic lower extremity PAD characterized by:
 - Fontaine Stage IIa - intermittent claudication after walking > 200 meters
 - Fontaine Stage IIb - intermittent claudication after walking < 200 meters
4. Have a mobile phone with Wifi and Bluetooth capability
5. Have a safe and suitable walking environment (e.g. safe sidewalks next to home)
6. Have the ability to read and speak the English language

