4.2.4 Intervention Group

The intervention group will receive the following 12-week step-based exercise prescription. The exercise goal of 5,000 daily steps is based on prior evidence demonstrating that a daily step count of less than 5,000 is associated with a negative impact on health²⁶.

- Week 1: walk at least 3,000 steps every day.
- Week 2: walk at least 3,500 steps every day.
- Week 3: walk at least 4,000 steps every day.
- Week 4: walk at least 4,500 steps every day.
- Weeks 5-12: walk at least 5,000 steps every day.

4.3 **Follow-up**

The study follow-up period will be 14 weeks. Week 1 will be a baseline assessment period during which we obtain baseline data. Weeks 2 through 13 will be the period of the study intervention. Week 14 will be the endpoint assessment period during which we obtain endpoint data.

Week 1

Discussed in Section 5.1 (Study Assessments, Baseline Assessment Period)

Weeks 2 to 13

Every 4 weeks of the 12-week exercise program: the study investigators will conduct both chart review and phone calls for all enrolled patients to assess for any drop-out criteria and adverse events. In addition, the study investigators will instruct patients regarding any concerning symptoms that should be reported to the study team or should require emergent medical attention (by calling 911). In order to assess compliance to the study protocol, all patients will transmit data from their fitness monitors to their online Fitbit accounts every 4 weeks.

Week 14

Discussed in Section 5.2 (Study Assessments, Endpoint Assessment Period)

5. Study Assessments

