5.1 Baseline Assessment Period

Week 1 will be the baseline assessment period, during which both the intervention group and the control group will wear their fitness monitors for 7 consecutive days. In addition to their usual daily activities, all patients will be instructed to walk continuously for at least one extended period of time on a daily basis. Given that this is a pilot study of a novel exercise program in PAD patients, the duration and frequency of these extended periods of time will be at the patients' discretion.

At the end of Week 1: the study investigators will conduct both chart review and phone calls for all enrolled patients to assess for any drop-out criteria and adverse events. In addition, the study investigators will instruct patients regarding any concerning symptoms that should be reported to the study team or should require emergent medical attention (by calling 911). Both groups will transmit the data from their fitness monitors to their online Fitbit accounts. Finally, both groups will also complete quality of life surveys (PAQ and VascuQol).

Prior to starting the Week 1 baseline assessment period, patients who undergo peripheral angiography will need to be cleared for full activity by the treating interventional cardiologist. The study investigators will ask the patients' treating interventional cardiologist 1 week after the procedure to verify the patients' clearance for full activity, and then call the patients with instructions to start the Week 1 run-in period.

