5.2 Endpoint Assessment Period

Week 14 will be the endpoint assessment period and will be structured identically to Week 1, during which both the intervention group and the control group will wear their fitness monitors for 7 consecutive days. In addition to their usual daily activities, all patients will be instructed to walk continuously for at least one extended period of time on a daily basis. Given that this is a pilot study of a novel exercise program in PAD patients, the duration and frequency of these extended periods of time will be at the patients' discretion.

At the end of Week 14: the study investigators will conduct both chart review and phone calls for all enrolled patients to assess for any drop-out criteria and adverse events. In addition, the study investigators will instruct patients regarding any concerning symptoms that should be reported to the study team or should require emergent medical attention (by calling 911). Both groups will transmit the data from their fitness monitors to their online Fitbit accounts. Finally, both groups will also complete quality of life surveys (PAQ and VascuQol).

6. Statistical Analysis

The primary endpoint of the mean daily walking distance (in steps) over 7 consecutive days will be assessed at baseline and at 3 months. Mean improvement in steps walked from baseline to 3 months will be calculated separately for the intervention and the control group. Noninferiority of the intervention group will be assessed by comparing mean improvement in steps walked, using a 1-sided t-test with a margin of noninferiority of 500 steps. Pedometry data from 22 patients with coronary artery disease undergoing 4 month behavioral intervention suggests the mean improvement in steps walked will have a standard deviation of 161 (VanWormer J, Boucher J, Pronk N, Thoennes J. Lifestyle behavior change and coronary artery disease: effectiveness of a telephone-based counseling program. *J Nutr Educ Behav*. 2004 Nov-Dec; 36(6):333-4.). With a sample size of 20 patients per group, we expect 90% power to demonstrate noninferiority of the intervention group (difference in mean improvement of -350 steps, which is within the margin of noninferiority).

The mean difference in the mean daily walking distance between the study groups will be analyzed by multiple linear regression, controlling for baseline mean daily walking distances. All outcomes will be analyzed by intention-to-treat.

7. Data Management

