9.1 Study Flow Diagram

9.2 **Control Group: Symptom-based Exercise Protocol**⁶⁻⁸

Week	Exact Dates *	Frequency	Exercise Prescription
1	(Run-in period)	Daily	Walk as much as possible
2		3-5 days a week	1. Walk on a flat surface at a constant speed for 45 consecutive minutes
3		3-5 days a week	2. Rest when you have leg pain (3 or 4 on a pain scale between 1 and 5, where 1 is no pain and 5 is severe pain)
4		3-5 days a week	3. Start walking when your leg pain has stopped
5		3-5 days a week	4. Repeat these walking/rest cycles
6		3-5 days a week	5. If you are able to walk for 8 minutes without stopping, increase your walking speed.
7		3-5 days a week	
8		3-5 days a week	
9		3-5 days a week	
10		3-5 days a week	
11		3-5 days a week	
12		3-5 days a week	
13		3-5 days a week	
14	(Endpoint period)	Daily	Walk as much as possible

* The exact dates will be written on the exercise prescription for each patient.

9.3 **Intervention Group: Step-based Exercise Protocol**

Week	Exact Dates *	Frequency	Exercise Prescription
1	(Run-in period)	Daily	Walk as much as possible
2		Daily	Walk at least 3,000 steps
3		Daily	Walk at least 3,500 steps
4		Daily	Walk at least 4,000 steps
5		Daily	Walk at least 4,500 steps
6		Daily	Walk at least 5,000 steps
7		Daily	Walk at least 5,000 steps
8		Daily	Walk at least 5,000 steps
9		Daily	Walk at least 5,000 steps
10		Daily	Walk at least 5,000 steps
11		Daily	Walk at least 5,000 steps
12		Daily	Walk at least 5,000 steps
13		Daily	Walk at least 5,000 steps
14	(Endpoint period)	Daily	Walk as much as possible

* The exact dates will be written on the exercise prescription for each patient.

10. References

3. McDermott MM. Lower extremity manifestations of peripheral artery disease: the pathophysiologic and functional implications of leg ischemia. *Circ Res*. 2015;116(9):1540-1550.

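### Is a 500-step non-inferiority margin too wide when the plan's own SD of change is 161 steps?

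*Combined protocol and SAP*

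**What the plan says.** Section 6 compares mean improvement in daily steps from baseline to 3 months, "using a 1-sided t-test with a margin of noninferiority of 500 steps". Pedometry from 22 coronary patients "suggests the mean improvement in steps walked will have a standard deviation of 161". With 20 per group the plan expects 90% power at a "difference in mean improvement of -350 steps, which is within the margin of noninferiority". It does not state alpha, why 500 steps was chosen, why a deficit of 350 is the planning case, or what gain the control arm is expected to make.

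Three other places bear on the reading:

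- **Assessment weeks.** In Week 1 (Section 5.1), and again in Week 14 (Section 5.2), "all patients will be instructed to walk continuously for at least one extended period of time on a daily basis". The schedules in Sections 9.2 and 9.3 say "Walk as much as possible" for both weeks in both arms.
- **Step target.** Section 4.2.4 asks the intervention arm, and only that arm, to "walk at least 5,000 steps every day" in the last eight weeks of the programme.
- **Purpose.** Section 1.2 calls the trial a pilot and adds: "We believe that this pilot study will generate data for a larger trial in the future".

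**The concern.** A margin of about three SDs of individual change is unusual, and so is planning on a deficit that uses up 70% of it (350/500). On the plan's own figures, and with normally distributed changes, a true deficit of 350 steps would leave about 98.5% of intervention patients improving less than the average control patient. The test would still pass such a programme in about nine trials out of ten.

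A non-inferiority margin takes its meaning from the benefit of the active control. Here that benefit is not given. Both arms are told to walk daily in the baseline week, so the control gain is measured on top of instructed walking and might be modest. If control gains 500 steps or fewer, a programme with no gain at all lies inside the margin. A pass would then say little about preserved benefit, and a later, larger trial might carry the same margin forward.

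**Working it through.** **Inputs (Section 6).** Margin 500, true difference -350, SD 161, n = 20 per group, one-sided t-test, stated power 90%. Alpha is not given, so one-sided 5% is assumed and 2.5% is shown beside it. SDs of 300 and 500 are assumptions used to show the range.

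**1. The plan's own figure.** Distance to margin = 500 - 350 = 150. Standard error = 161 × √(2/20) = 50.9. Noncentrality = 150/50.9 = 2.95 on 38 df. Power from the noncentral t is 89.4% at one-sided 5% and 81.9% at 2.5%. The normal approximation at 5% gives 90.3%. The stated 90% is therefore reproduced at one-sided 5%.

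**2. Margin in SD units.** 500/161 = 3.11 and 350/161 = 2.17; Φ(2.17) = 98.5%.

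**3. The equal-power result.** A margin of 150 at a true difference of 0 has the same distance, 150 - 0 = 150, and so the same noncentrality and the same 89.4%. This is an identity that holds at any alpha. It shows that power depends on distance to the margin. It does not show which margin is acceptable.

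**4. What a pass would allow.** The largest observed shortfall that passes at one-sided 5%, if the observed SD is 161, is 500 - 1.686 × 50.9 = 414 steps a day. At 2.5% it is 500 - 2.024 × 50.9 = 397.

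**5. What the wider margin protects against.** Power with 20 per group, one-sided 5%:

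| SD of change | 500 margin, true -350 | 500 margin, true 0 | 150 margin, true 0 |
|---|---|---|---|
| 161 | 89% | >99.9% | 89% |
| 300 (assumed) | 46% | >99.9% | 46% |
| 500 (assumed) | 24% | 93% | 24% |

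The first and third columns agree because both distances are 150. If the programmes are equal, the 500-step margin keeps 90% power up to an SD of about 531; the 150-step margin keeps it only up to about 159. At SD 161, a true deficit of just 50 steps cuts the 150-step margin's power to 61%. With the 500-step margin it stays above 99.9%.

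**6. Cost of a narrower margin at a stricter alpha.** At one-sided 2.5%, SD 161 and 20 per group, a 150-step margin has 82% power at a true difference of 0 and 48% at -50. It needs 26 per group for 90% at 0. At SD 300 or 500 it needs 86 or 235 per group.

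**7. Precision whatever the margin.** The expected half-width of a two-sided 95% interval, unadjusted, is 2.024 × 50.9 = 103 steps at SD 161, and 192 and 320 steps at SDs of 300 and 500.

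**The case for a change.** The strongest case for a change is that the plan cannot have it both ways. If 161 is right, the margin is 3.1 SD. If 161 is too small, the margin looks less extreme but the stated power at -350 is lost, since 90% there needs an SD of about 160 or less. There is reason to doubt 161: it comes from coronary rather than PAD patients, and entry is by symptoms (for example "Fontaine Stage IIa - intermittent claudication after walking > 200 meters") with no baseline step range. The remedy offered would be either to drop the non-inferiority conclusion and report an estimate, or to tie a tighter margin to the control gain.

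Part of this stands. The 500 and the 350 are unexplained, no control gain is given, and the 90% depends on the SD. The rest is weaker:

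- **SD units do not settle the margin.** How many steps a day may be given up is a clinical question in absolute terms. The only scale in the documents is Section 4.2.4, where 500 steps is one weekly increment and 10% of the 5,000-step goal. The plan does not offer this as its rationale, but it shows that the number is not out of scale with the programme.
- **The extra width is not idle.** Step 5 shows that it protects against a larger SD and against small true deficits.
- **The doubts about 161 cannot be taken further here.** Reading it as a standard error cannot be checked without the cited study, and taken as an individual SD it reproduces the stated power. Nor does the 5,000-step goal imply a common end value: it applies to one arm, is a minimum, and ends before Week 14.
- **The remedies have real costs.** Dropping the conclusion removes the hypothesis in Section 1.2. A tighter margin costs power or patients (step 6), and the control gain needed to set it is not in the documents.

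**Conclusion.** No change to the plan follows. The margin is 3.1 times the assumed SD and the equal-power result is exact, but neither is an error: the stated 90% is reproduced at 89.4%, on the assumption of one-sided 5%. The wide margin is a debatable trade-off. On an SD of 161 it would let an observed shortfall of up to about 414 steps a day pass. In return, a 40-patient trial keeps 93% power for equal programmes even if the SD is as large as 500.

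The supportable criticism is narrower: Section 6 does not justify 500 or 350, and it states neither alpha nor the expected control gain. Analysts can fill that gap sensibly when reporting. Section 6 already plans a regression adjusted for baseline, which yields the estimated difference and its interval, and Section 6 also calculates each arm's mean improvement. A reader can set the interval against any smaller margin and against the gain actually seen in the control arm. A pass should be read as preserved benefit only if that gain is clearly above 500 steps.

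This conclusion rests on the trial being a pilot and on the documents giving no control gain. With a sourced gain well below 500 steps, the margin itself would be open to challenge.

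### Does the stated 90% power need correcting because it rests on an unstated alpha, no patient loss and a standard deviation taken from 22 patients?

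*Combined protocol and SAP*

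**What the plan says.** Section 1.2 sets the total: "We will enroll and randomize 40 patients to a novel 12-week step-based exercise program" or to the symptom-based comparator. It calls the trial a pilot meant to inform a larger one. The split into 20 per group appears only in Section 6.

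Section 6 compares mean improvement in daily steps between groups "using a 1-sided t-test with a margin of noninferiority of 500 steps". For the variability it relies on an outside study: "Pedometry data from 22 patients with coronary artery disease undergoing 4 month behavioral intervention", which it says "suggests the mean improvement in steps walked will have a standard deviation of 161". The power claim, "With a sample size of 20 patients per group, we expect 90% power to demonstrate noninferiority of the intervention group", is tied to one scenario: "difference in mean improvement of -350 steps, which is within the margin of noninferiority".

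Two further sentences matter. The group difference in walking distance "will be analyzed by multiple linear regression, controlling for baseline mean daily walking distances", and "All outcomes will be analyzed by intention-to-treat". Section 3.3 lists 21 drop-out criteria and three adverse events that lead to discontinuation from the study.

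The documents do not state an alpha level, the confidence bound that decides non-inferiority, an expected loss rate, a method for a missing Week 14 step count, or a baseline correlation.

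**The concern.** At the planning scenario only 500 - 350 = 150 steps separate the assumed truth from the margin. Power there is sensitive to anything that widens the standard error, and three inputs look weak:

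- **Alpha.** Only the sidedness is given. A dataset could pass against a one-sided 95% bound and fail against a 97.5% bound.
- **Evaluable patients.** The 40 randomized are exactly the 2 x 20 in the power statement. Section 3.3 makes some discontinuation plausible, and intention-to-treat is not accompanied by a rule for missing step counts.
- **SD.** The 161 is a point estimate from 22 patients with a different disease in a different program, and nothing is said about why it should carry over.

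If all three turned out unfavourably, a truly non-inferior program could fail its test well over 10% of the time. Readers would have taken 90% as firmer than it is.

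**Working it through.** **Inputs (all from Section 6):** margin 500, true difference -350, SD 161, 20 per group, one-sided two-sample t-test. Alpha is not given, so the usual levels are tried.

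**1. Reproduce the stated figure.**

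- Standard error = SD x sqrt(2/n) = 161 x sqrt(2/20) = 50.9.
- Standardized distance to the margin = (500 - 350)/50.9 = 2.946.
- Normal approximation: power = Phi(2.946 - z), with z the one-sided critical value. At 0.05, Phi(2.946 - 1.645) = 90.3%.
- Exact: noncentral t with 20 + 20 - 2 = 38 degrees of freedom and noncentrality 2.946.

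| One-sided alpha | Normal | Exact t |
|---|---|---|
| 0.10 | 95.2% | 94.9% |
| 0.05 | 90.3% | 89.4% |
| 0.025 | 83.8% | 81.9% |

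The plan's 90% with 20 per group matches 0.05 and neither of the other levels. By the normal approximation 20 per group is also the sample size required at 0.05; by exact t it is 21.

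**2. Loss (SD 161, alpha 0.05, exact t).** The documents give no loss rate, so these group sizes are assumptions.

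| Evaluable | Power |
|---|---|
| 20 and 20 | 89.4% |
| 20 and 19 | 88.7% |
| 19 and 19 | 87.9% |
| 18 and 18 | 86.3% |
| 16 and 16 | 82.4% |

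One lost patient costs 89.4 - 88.7 = 0.7 points. By the normal approximation, which the plan's figure matches, 20 and 19 still give 89.7%. Losing two per group costs 89.4 - 86.3 = 3.1 points.

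**3. Sampling error of the SD.** For normal data, the 95% limits are 161 x sqrt(21/chi-square quantile) with 21 degrees of freedom, which gives 124 to 230. Both limits must be shown. With 20 per group at 0.05 (exact t):

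- SD 124: 98.3%
- SD 161: 89.4%
- SD 230: 64.8%

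Averaging power over 161 x sqrt(21/chi-square with 21 df) gives 86.7%, which is 89.4 - 86.7 = 2.7 points below the point-estimate value.

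**4. Are the three conditions jointly necessary?** No, they trade off (true difference -350, exact t):

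- SD 140, 16 per group, alpha 0.05: 90.6%
- SD 140, 20 per group, alpha 0.025: 91.0%
- SD 124, 16 per group, alpha 0.025: about 91%

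All these SDs lie inside the 124 to 230 interval. So 90% does not require alpha 0.05, full retention and an SD of at most 161 together.

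**5. How demanding is the planning scenario?** With 20 per group, alpha 0.05 and SD 230, power is 64.8% at -350, 85.4% at -300, 95.8% at -250 and above 99% at no true difference. With no true difference, 90% power holds up to an SD of about 531.

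**6. Baseline adjustment.** If the regression leaves a residual SD of SD x sqrt(1 - r^2), where r is the correlation of change with baseline, and one degree of freedom is lost, 90% at -350 and alpha 0.05 returns with |r| of about 0.35 (SD 161, 18 per group) or 0.72 (SD 230, 20 per group). The plan gives no value of r, so this shows a possible gain and cannot be credited.

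**The case for a change.** The strongest case for acting is that wording costs almost nothing. A formal non-inferiority test should name its error rate, and a reader should not have to recover it by solving a power statement backwards. Intention-to-treat alongside required discontinuation leaves the evaluable number open. The SD comes from coronary patients in a four-month program, and even in a pilot a declared margin and power invite a confirmatory reading.

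Part of this stands. The alpha and the missing-data method are absent, and I found neither elsewhere in the documents. A protocol that stated both would be better written.

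The rest does not carry a change. The stated power is not wrong: it follows from the stated inputs at a conventional level. The loss rates that lower it are assumed. The SD could be too small or too large, and the documents offer no second value. Whether 161 applies to these patients, or what exactly it measures, can be settled only from the cited source. The plan discloses that source along with its disease, size and duration. A table of power against SD and retention would describe uncertainty already evident from 22 patients, and would alter neither the design nor the analysis.

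**Conclusion.** No change is needed. On the plan's own inputs the 90% reproduces at one-sided 0.05 (90.3% normal approximation, 89.4% exact t). It should be read as conditional on an SD of 161 and 20 evaluable patients per group. Within that reading it is moderately sensitive to loss (86.3% with 18 per group, 82.4% with 16, both assumed) and more sensitive to the SD, in both directions (98.3% at 124, 64.8% at 230).

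The two real omissions are gaps of detail. The power statement itself points to one-sided 0.05, so the matching decision rule is a lower one-sided 95% confidence bound above -500 steps for intervention minus control. An analyst can also choose and report a reasonable treatment of missing Week 14 step counts. Neither gap makes a stated figure wrong or calls for a different method.

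This conclusion assumes that 161 is a patient-level SD of change, as the plan's calculation treats it, and that step changes are roughly normal for the SD interval. If the trial were meant to use one-sided 0.025, the same inputs would give 81.9% and the stated 90% would not hold. Nothing in the documents suggests that level.

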
In contrast, home exercise programs offer an alternative treatment strategy that is more feasible for patients. Home exercise programs have also demonstrated significant efficacy of improving maximal walking ability for symptomatic PAD patients ¹⁷⁻²⁴, and are based on the standard symptom-based exercise protocol without direct supervision ^{5-9,17-24}. Limitations to home exercise programs include the inability to objectively monitor exercise capacity at home in the absence of a treadmill, variable adherence rates to the standard protocol in the absence of direct supervision, and variable adherence rates to the performance of exercise for 45 minutes, 3 to 5 days a week, in the absence of a supervised program. In order to address these limitations, several investigators have studied the utilization of a fitness monitor during symptom-based home exercise sessions ¹⁷⁻²¹.

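### Non-inferiority is judged by intention-to-treat alone; some patterns of non-adherence can then hide a deficit of more than 500 steps in patients who follow the programme

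*Combined protocol and SAP*

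**What the plan says.** Section 1.2 describes a "single-center prospective non-inferiority randomized controlled trial". Section 6 compares mean improvement in steps "using a 1-sided t-test with a margin of noninferiority of 500 steps" and closes with "All outcomes will be analyzed by intention-to-treat". No per-protocol set, adherence threshold, estimand or adherence-based sensitivity analysis appears anywhere in the document.

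Three other places bear on this:

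- Section 1.1.1 lists "variable adherence rates to the standard protocol in the absence of direct supervision" among the limitations of home programmes. Both arms here are home programmes.
- Section 4.3 collects the relevant data at 4-week intervals: "In order to assess compliance to the study protocol, all patients will transmit data from their fitness monitors". Section 6 does not use them.
- Section 7 has the online data destroyed once the data analysis is complete.

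**The concern.** In a superiority trial, dilution by non-adherence usually works against the sponsor's claim. In a non-inferiority trial it can work in favour of the claim. If a share of patients in both arms do not follow their programme and end up alike, the intention-to-treat difference is smaller than the difference among patients who do follow it. A programme that is worse by more than 500 steps when followed could then pass the test. The stake is what the trial's conclusion would mean, in a pilot that Section 1.2 intends as the basis for a larger trial.

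**Working it through.** **Inputs from Section 6.** The margin is 500 steps. The planning data are said to show that the change "suggests the mean improvement in steps walked will have a standard deviation of 161". The sample size and power are given as "With a sample size of 20 patients per group, we expect 90% power to demonstrate noninferiority of the intervention group", for a "difference in mean improvement of -350 steps, which is within the margin of noninferiority". The alpha level is not stated.

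**Step 1: reproduce the stated power.** The standard error of the difference is 161 × √(2/20) = 50.9. The distance from the assumed difference to the margin is 500 − 350 = 150, and 150/50.9 = 2.95.

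- One-sided 0.05: Φ(2.95 − 1.645) = 90.3%; the noncentral t with 38 df gives 89.4%.
- One-sided 0.025: 83.8% (normal) or 81.9% (t).

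The stated 90% therefore implies one-sided 0.05, which is used below.

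**Step 2: dilution.** The document gives no adherence rate, so every adherence input here is an assumption. Let q be the non-adherent share, equal in both arms, with no between-arm difference among non-adherers. Then:

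intention-to-treat difference = (1 − q) × difference when followed.

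For a deficit of 600 when followed and q = 30%, this is 0.7 × (−600) = −420, inside the margin. A 600-step deficit crosses inside once q exceeds 1 − 500/600 = 16.7%.

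**Step 3: chance of declaring non-inferiority, SD held at 161.** The noncentrality is (500 − deficit)/50.9.

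| Intention-to-treat difference | Noncentrality | Chance |
|---|---|---|
| −600 (q = 0) | −100/50.9 = −1.96 | 0.02% |
| −420 (q = 30%) | 80/50.9 = 1.57 | 46% |

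**Step 4: add the mixture variance.** Mixing adherers who improve by m with non-adherers who do not change adds q(1 − q)m² to the variance in that arm, so the 46% is too high. With q = 30%, q(1 − q) = 0.21, and 161² = 25,921.

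| Control adherers improve by (assumed) | Step adherers improve by | Control-arm variance | Step-arm variance | SE of difference | 80/SE |
|---|---|---|---|---|---|
| 600 | 0 | 25,921 + 75,600 = 101,521 | 25,921 | √(127,442/20) = 79.8 | 1.00 |
| 1,000 | 400 | 25,921 + 210,000 = 235,921 | 25,921 + 33,600 = 59,521 | √(295,442/20) = 121.5 | 0.66 |

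With the critical value t = 1.686, a normal approximation gives Φ(1.00 − 1.686) ≈ 25% and Φ(0.66 − 1.686) ≈ 15%. Simulating the t-test itself gives about 23% and 13%.

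**Step 5: other SDs.** Even with mixture variance ignored, the rise at an assumed SD of 500 is from 1.2% to 12.6%, and at 1,000 from 2.5% to 8.1%.

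**Step 6: unequal non-adherence.** Assume a 500-step deficit when followed, control adherers improving by 1,000, and 20% non-adherence in one arm only.

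- Control arm only: 500 − 0.8 × 1,000 = −300. Non-inferiority is declared in about 61% of simulated trials.
- Step arm only: 0.8 × 500 − 1,000 = −600. It is declared in about 0.1–0.2%.

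The direction of the effect therefore depends on where the non-adherence falls.

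**The case against.** The strongest reply concerns the question being asked. Both programmes are home prescriptions and the endpoint is free-living daily steps. If the aim is the effect of prescribing the programme, a true intention-to-treat difference of −420 really is within the margin, and declaring non-inferiority is no error. That stands, and it is why intention-to-treat should remain primary. What is missing is a statement of which effect is meant, and any support for the other one.

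A reader might go further and infer that non-adherence must pull the arms together. Step 6 shows that it need not. A reader might also infer that the trial could not tell two equally effective programmes from two that nobody followed. The document does not support that: Section 6 calculates mean improvement separately in each arm, so two arms with little change would be visible, and compliance data exist.

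A per-protocol analysis also has its own hazards. If step-arm adherence means reaching step targets, the set is selected on something very close to the week-14 step count, while the control arm would be selected on something else; that can favour non-inferiority. A rule requiring 45 active minutes would misclassify control patients who take the rests built into their prescription (Section 4.2.3 and Appendix 9.2). Section 4.2.2 cites validation of the device for step counts only; the remark about activity time in Section 1.1.2 concerns fitness monitors in general. These points limit how adherence can be defined and how much weight the analysis can carry. They do not remove the case for planning one.

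**Conclusion.** The point holds as a gap in supporting analysis. It does not show that intention-to-treat is the wrong primary analysis, nor that a non-inferiority finding would be invalid. If non-adherence is similar in both arms or concentrated in the control arm, the planned test can declare non-inferiority for a programme that is worse by more than 500 steps when followed. In the illustration the chance goes from 0.02% to about 13–23%. The 46% obtained without mixture variance should not be quoted as the size of the problem.

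The result rests on an assumed 600-step deficit, an assumed 30% non-adherence in both arms, no change among non-adherers, assumed control improvements of 600–1,000 steps, the planning SD of 161, and an inferred one-sided 0.05. The rise shrinks at larger SDs, and the effect can reverse if only the step arm fails to adhere.

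**What to change.** Keep intention-to-treat as the primary analysis and say that it estimates the effect of prescribing the programme. Then, before any outcome analysis:

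1. Define adherence in each arm from the monitor data synced every 4 weeks. The definition should be as comparable across arms as the data allow, should not simply select on the step-count outcome, and should allow for the control arm's rest periods.
2. Add a supportive per-protocol or complier-type analysis with the same 500-step margin and one-sided bound. Report whether it agrees with intention-to-treat, and interpret any disagreement cautiously.
3. Report adherence by arm next to each arm's mean improvement. This would also serve the feasibility aim in Section 1.2, for which Section 2 lists no endpoint.
4. Derive the adherence variables before the online data are destroyed under Section 7.

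The cost is one definition and one further analysis of data already being collected. The adherent set is smaller and not protected by randomisation. If 30% per arm are excluded (14 left per arm), power at −350 with SD 161 falls from 89.4% to about 77%, even if the exclusions are unrelated to outcome. The analysis can therefore only be supportive.
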